3. STUDY OBJECTIVES

Primary objective:

To compare a high-dose rifampicin standard TB regimen of 6 months duration with standard TB regimen with respect to adverse treatment outcome (relapse, failure, death and default) and toxicity, in TB cases (new or retreatment, pooled) not shown to have initial rifampicin resistance before one of the standard treatment outcomes applies.

Secondary objectives:

1. To assess whether the study regimen also cures low-level rifampicin resistant TB: by comparing and describing adverse treatment outcomes by initial rifampicin mutations (none, low-level, high)
2. To assess the effectiveness of FDA vital staining screening at two weeks of treatment for early switch of non-responding rifampicin resistant TB to MDR-TB treatment, versus clinical evaluation based on fever resolution. The proportions of rifampicin resistant cases started on MDR treatment within the first 2 months of primo-treatment as well as the proportion of initially present resistance never switched to the MDR regimen and not cured will be compared between the two arms.
3. To assess the negative predictive value of conversion at 2 weeks for relapse
4. To estimate the proportion of acquired rifampicin resistance among failures and relapses
5. To compare the predictive value of auramine with FDA staining at 2 weeks to predict unfavourable outcomes

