8.4 Sample size and power

The sample size of two times 500 patients is a trade-off between precision and exposing an excessively high number of patients to potentially more toxic treatment. Power has not been taken into account, but if the results are favourable large scale cluster-randomized study will be designed to bring definitive proof.

The registered incidence of clinically apparent hepatitis from any cause during TB treatment is 1.5% for the study population. With the proposed sample size, an increase by at least 2% compared to the control arm will attain statistical significance ($p=0.047$).

With the standard (=control) regimens and definitions, about 2% failures and 2% relapses are currently notified by the DF project, but only 50% of those are culture-positive, and about half of the culture positive failures and relapses are rifampicin-resistant. Overall cure rate (new and retreatment cases together) is close to 90%, with 4% default and 4% deaths. Based on the data from 2010 about 20 cases with rifampicin resistance may be enrolled, 10 in each arm. We estimate that the more effective study regimen plus early detection of serious drug resistance rolled over to MDR-TB

treatment will prevent drug resistant failure and relapse, reduce rifampicin susceptible relapse to an estimated two third, and reduce death and default because of unrecognized rifampicin resistance to 80% of the control arm. This total estimated reduction of unfavourable outcome from 10% to 7% remains non-significant with the targeted enrolment of two times 500 cases. With 80% power and 95% confidence level, 2 x 1421 patients would have to be enrolled, which is not feasible and also difficult to justify. However, a slightly larger reduction of unfavourable outcome from 10% to 6.5% comparing two arms of 500 cases each would already result in a significant p-value. Additional evidence will be obtained studying *rpoB* mutations, initially (all smear-positives) and at time of failure or relapse (only in the few such cases expected). Absence of low-level resistance mutations only among patients with unfavourable outcome on the high-dose arm, while they were present among new cases in both arms, will be interpreted as additional evidence of effectiveness of the increased dosing.

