#### *4.1.1. Intention to treat (ITT) analysis*

In the Intention-to-Treat analysis, all patients will be analysed according to their randomized allocation, even in case they receive another treatment regimen, show protocol violations prior to or during the study. Patients lost-to-follow-up before the 12 month post treatment follow-up or who do not provide a sputum are considered to be adverse treatment outcomes in this analysis, unless they are known to have moved out of the study region.

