#### 4.2. Efficacy study endpoints

##### *Primary endpoint*

The primary efficacy endpoint is the incidence of adverse treatment outcomes. Following the WHO guidelines from 2010, as currently in use in the NTP in Bangladesh, an adverse treatment outcome is defined as any occurrence of the following:

- Relapse: Cured previously from TB or completed treatment for TB and now having bacteriologically positive sputum for TB (at 12 months follow-up or at an earlier time point)
- Default: The patient whose treatment was interrupted for 2 consecutive months or more.

- Failure: Sputum positive for TB at 5 months or later during treatment. Failure will also be declared if the regimen has to be changed for at least 2 drugs due to adverse events.
- Death: All-cause mortality between case registration and end of TB treatment (related or not to TB or TB treatment)

Patients who are transferred out will be excluded from the outcome analysis.

In line with current WHO recommendations, patients detected with MDR-TB or rifampicin resistance before any outcome applies and switched to the MDR-TB regimen will be excluded from the outcome analysis.

Analyses will be performed using the NTP smear-based recurrence (failure, relapse) definitions, but as a secondary approach culture-based definitions will be used. In each analysis, if a patient has two events for the analysis of interest, the first endpoint will be taken into account, except for cured/completed followed by relapse which is considered as relapse.

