#### *Secondary endpoints*

Secondary objectives are assessed with the adverse treatment outcomes defined above.

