7.4. To estimate the proportion of acquired rifampicin resistance among failures and relapses

Proportions per treatment arm will be estimated together with 95% Wilson confidence intervals, using the number of failure / relapse cases without mutation detected at diagnosis as the denominator.

7.5. To compare the predictive value of auramine with FDA staining at 2 weeks to predict unfavourable outcomes

The ROC curves of auramine resp. FDA staining at 2 weeks to predict adverse treatment outcome will be plotted and compared using the nonparametric approach of DeLong, DeLong, and Clarke-Pearson (1988). In addition, the proportion of referrals to rapid DST will be compared between auramine and FDA using the chi-squared or Fisher exact test.

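### SAP 7.5 compares the two stains only on a composite that is about two thirds default and all-cause death; a failure/relapse ROC comparison should be added beside it

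*SAP*

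**What the plan says.** SAP 7.5 covers the objective "To compare the predictive value of auramine with FDA staining at 2 weeks to predict unfavourable outcomes" (Protocol section 3, objective 5). Its main analysis is: "The ROC curves of auramine resp. FDA staining at 2 weeks to predict adverse treatment outcome will be plotted and compared", using the paired nonparametric DeLong method. It then compares how many patients each stain would refer for rapid DST. No other outcome is given for the ROC analysis and no analysis population is named.

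The SAP text on secondary endpoints confirms the outcome: "Secondary objectives are assessed with the adverse treatment outcomes defined above". SAP 4.2 lists its parts as relapse, default, failure and death. Failure includes a regimen change of at least two drugs for adverse events. Death is from any cause up to the end of treatment. Patients found rifampicin-resistant before an outcome applies and switched to the MDR regimen are excluded. SAP 4.1.1 adds to the composite, under intention to treat, patients lost before the 12-month visit or "who do not provide a sputum are considered to be adverse treatment outcomes in this analysis", unless they are known to have left the area.

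Protocol 8.4 gives the expected mix under the standard regimens: "about 2% failures and 2% relapses are currently notified by the DF project", and a cure rate that "is close to 90%, with 4% default and 4% deaths". SAP 2.1 has both stains read at week 2 in the intervention arm only, so the ROC analysis rests on about 500 patients.

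**The concern.** A week-2 bacillary count measures early bacteriological response. It has a direct reason to predict failure and relapse. It has a weaker reason, or none, to predict default, a missed sputum at 12 months, death from any cause, or a failure declared because drugs were changed for toxicity. In a ROC analysis such events behave like mislabelled cases: they lower both AUCs and narrow the difference between them.

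What is at stake is how the stain comparison is read. Protocol 2.1 says that the trial will help adapt the resistance-screening algorithm of a larger study. If the only pre-specified curves use the composite, similar low AUCs could mean that the stains perform alike, or that most of the events were ones neither stain could foresee. The plan offers no analysis within objective 5 to tell these apart.

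**Working it through.** **Nearest stated figure.** The documents give no AUC, power or event count for SAP 7.5. The closest figure is Protocol 8.4's 1421 per arm for 10% v 7% unfavourable outcome. The standard two-proportion formula (two-sided 5%, 80% power) gives 1356 without and 1422 with continuity correction, so the stated figure is reproduced to within one patient.

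**Share of death and default**
- Programme rates: (4 + 4) / (2 + 2 + 4 + 4) = 8/12 = 67%. The protocol's 10% total equals 2 + 4 + 4, without relapse; against that total the share is 8/10 = 80%.
- Intervention arm, on the protocol's own expectations: half of the 4% failure/relapse is culture-positive and half of that is resistant, so 1% is resistant (0.5% failure, 0.5% relapse, assuming an even split). If this is prevented and susceptible relapse falls to two thirds, failure is 1.5% and relapse 1.5% × 2/3 = 1.0%, together 2.5%. With death and default at 6.4% (8% × 0.8) to 8%, the share is 6.4/8.9 = 72% to 8/10.5 = 76%.
- Lost and no-sputum patients come on top.

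**Effect on the AUCs.** With w the share of failure/relapse among events:

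AUC(composite) = w × AUC(failure/relapse) + (1 − w) × AUC(other events)

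Assume AUCs of 0.85 (FDA) and 0.70 (auramine) for failure/relapse, 0.50 for other events, and w = 20/60 = 1/3:
- FDA: 0.85/3 + 0.50 × 2/3 = 0.617
- auramine: 0.70/3 + 0.50 × 2/3 = 0.567
- gap: 0.15 becomes 0.05.

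**Effect on power.** The composite has three times as many events, which offsets part of the loss. A simulated paired DeLong test (500 patients, binormal scores, correlation between stains 0.6, 2,000 replicates, two-sided 5%) gives the following. The failure/relapse analysis leaves out the other events; the composite keeps them. AUCs and correlation are assumptions, and repeat runs differ by two or three points.

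| Events: failure/relapse + other | AUC of stains for other events | 0.85 v 0.70: composite / failure-relapse | 0.80 v 0.70: composite / failure-relapse |
|---|---|---|---|
| 20 + 40 | 0.50 / 0.50 | 28% / 87% | 15% / 50% |
| 20 + 40 | 0.55 / 0.525 | 46% / 85% | 30% / 51% |
| 20 + 40 | 0.60 / 0.55 | 67% / 86% | 49% / 49% |
| 20 + 40 | 0.65 / 0.58 | 79% / 85% | 67% / 53% |
| 20 + 85 (45 no-sputum, 9% assumed) | 0.50 / 0.50 | 16% / 85% | 9% / 50% |
| 12 + 34 (nearer the intervention-arm expectation) | 0.50 / 0.50 | 17% / 67% | 10% / 37% |

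A wider grid (FDA 0.75 to 0.90, auramine 0.65 to 0.70, correlation 0.5 to 0.85, other events unrelated) shows the composite keeping about 23% to 57% of the failure/relapse power, with one extreme case at 76%.

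**Culture-negative events.** Protocol 8.4 says that only half of notified failures and relapses are culture-positive. If the culture-negative half carries no signal (assumption), then for 0.85 v 0.70 smear-based failure/relapse (10 + 10) has about 25% power against 10% for the composite. Ten culture-confirmed events give about 61% against 13%; five give about 38%.

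**The case against.** The case for leaving SAP 7.5 alone has four parts.

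1. **The SAP follows the protocol.** Objective 5 names unfavourable outcomes. Replacing the composite would change the endpoint of a protocol objective. This stands, and is why the composite should be kept.

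2. **Death and default need not be unrelated to the smear.** Protocol 1.1 says that patients with unrecognised MDR-TB may die or default, and Protocol 8.4 expects earlier detection to reduce both. This stands in part. About 10 resistant cases are expected per arm, against about 40 deaths and defaults per 500 (8%). So even if all ten died or defaulted, roughly three quarters of these events would arise by another route. Detected and switched cases are also excluded from the outcome analysis. Extensive disease could still leave some link, and the table shows that a moderate one largely removes the loss; a stronger one can favour the composite.

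3. **Failure and relapse are few.** Twenty events is a smear-based count at standard-regimen rates. The intervention arm may have about 12, and perhaps 5 to 10 culture-confirmed. The 87% is therefore an upper-end figure. This stands, although in the scenarios with unrelated deaths and defaults the failure/relapse analysis remains ahead.

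4. **The trial is a pilot aimed at estimation, and other analyses help.** SAP 7.3 looks at relapse among early converters, Protocol 8.3.4 compares the stains' sensitivity for initial resistance, and the per-protocol set removes missing endpoints. None of these compares the two stains on failure and relapse. Because estimation is the aim, an AUC diluted by unrelated events is a problem whatever the power.

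A reader might infer that the composite pulls both AUCs down to 0.5 and necessarily costs most of the power. The documents do not support that: the areas move toward 0.5 (0.62 and 0.57 in the example), and the size of the loss depends on an independence that the plan neither states nor fully implies.

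**Conclusion.** The point holds as a cheap improvement. The outcome in SAP 7.5 is about 67% default and all-cause death on the programme rates, and about 72% to 76% on the protocol's expectations for the intervention arm, before lost and no-sputum patients are added. If those events are unrelated to the week-2 smear, the AUC gap falls to about one third and power from 87% to 28% (0.85 v 0.70), or from 50% to 15% (0.80 v 0.70). With linked AUCs of 0.60 and 0.55 for death or default, the comparison is 86% v 67% in the first case and equal in the second.

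The stain AUCs, their correlation, the AUCs for other events and the 9% no-sputum rate are all assumptions. Only the event rates and the arm size come from the documents. The direction of the dilution is firm for events unrelated to the smear; its size is not. The point concerns one secondary objective and does not touch the primary analysis.

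**What to change.** In SAP 7.5:

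- Keep the ROC comparison on the composite adverse outcome, as the protocol objective names it.
- Add beside it a pre-specified paired DeLong comparison with bacteriological failure or relapse as the event: smear-based, with culture-based as the secondary version, matching SAP 4.2. Deaths, defaults, lost or no-sputum cases and failures declared for adverse-event regimen changes do not count as events and are left out of this analysis.
- Name the analysis population for both comparisons, and report each AUC and the difference with 95% confidence intervals.
- Base any statement about which stain better identifies bacteriological non-response on the failure/relapse analysis.

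**Cost.** A few lines of SAP text. The outcome categories and stain results are already collected, and SAP 7.4 already works with failures and relapses as a group. There are two drawbacks. With about 20 events or fewer, and perhaps 5 to 10 culture-confirmed, the interval for each AUC will be wide. Leaving out deaths and defaults also conditions on what happened after baseline, which could select patients if some of those events reflect poor response. Showing the two analyses side by side lets the reader judge that.

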7.6. To compare weight gain and fever resolution between the two regimens

Weight gain between enrollment and end of treatment will be compared between the two regimens using the t-test or Wilcoxon rank sum test, as appropriate. Fever resolution after two weeks of treatment will be compared between the two regimens using the chi-squared or Fisher's exact test.

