 - Rifampicin sensitive:
 - Control arm: start Cat. 2
 - Intervention: re-start Cat. 1
 - Enquire, register adverse effects. Stop all drugs and refer in case of hepatitis suspicion (feeling sick, anorexia, vomiting, jaundice)
- Visit after 6 months (or 8 months for Cat. 2) V8: intervention + control arm
 - Clinical check, weight, temperature: signs and symptoms of TB absent?
 - Stop treatment, record attendance
 - Sputum smear for AFB: all patients
 - Declare cured if negative and inform about signs of relapse
 - Declare failure if positive and refer for rapid DST if AFB-positive

- Switch to MDR treatment if rifampicin resistant
- Rifampicin sensitive:
 - Control arm: re-register, start Cat. 2
 - Intervention: re-register, re-start Cat. 1
- Enquire, register adverse effects
- Make appointment for check-up after 12 months

- Visit 12 months after end of treatment V9 (intervention + control arm cured or defaulted)

- Reminders, home visit if not attending
- History from relatives / neighbours if not met (retreated or died of TB?)
- Clinical check: signs and symptoms of TB absent?
- If attending at the clinic only: weight, temperature
- Sputum smear and culture for AFB
 - If negative: further passive follow-up
 - If positive: declare relapse and refer for rapid DST
 - Switch to MDR treatment if rifampicin resistant
 - Rifampicin sensitive:
 - Control arm: re-register, start Cat. 2
 - Intervention: re-register, re-start Cat. 1

All enrolled patients will be monitored intensively for drug toxicity (clinical; liver enzymes during the first 2 months). Treatment will be interrupted in case of a serious adverse event, possibly due to the TB drugs, and patients referred to the nearest project hospital. In case of toxic hepatitis, after full recovery drugs will be re-introduced in hospital one by one, aiming at re-starting the same regimen since this toxicity is often transient and probably not rifampicin dose-related.

Unscheduled visits can take place at any time during the patients participation in the study. During these visits, all study procedures will be performed if needed, and data will be collected.

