2) Assessment of drug toxicity and initial treatment response will be performed at the time the last recruited patient finishes treatment. The data will be compiled at 9 months after the end of recruitment to ensure all treatment related data, including 8 months of treatment for retreatment cases in the control arm, are available. This analysis will be primarily performed for the go/no-go decision and design considerations for a possible next study, such as a cluster-randomized trial. The decision on proceeding to the cluster randomized study will be based on the absence of excess toxicity, a trend toward a reduction of unfavourable outcomes (excluding relapse), possible favourable effects overcoming low-resistance mutations.

3) A final analysis of the study endpoints, including relapse, will be performed one year after end of treatment of the last enrolled patients, i.e. about 2.5 years after enrolment start.

This analysis plan will be finalized and approved before database lock of the first interim analysis data. Major changes in statistical methodology used for the main and pre-planned analyses from this SAP, will require detailed description and justification in the statistical analysis report. The final analysis datasets, programs, and outputs are archived following good clinical practice guidelines (ICH E9).

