#### Treatment:

*New cases:* 2HRZE/4HR, i.e. 2 months of isoniazid, rifampicin, pyrazinamide and ethambutol intensive phase, followed by 4 months continuation phase isoniazid plus rifampicin) (Cat. 1 regimen, 6 months)

*Retreatment cases:* 2 months of SHRZE (S= streptomycin) followed by 1 month of HRZE and 5 months HRE (Cat. 2 regimen, 8 months)

Any patients with *MDR TB detected* at any time will be switched to 4KHPtoGCEZ/5GCEZ, i.e. 4 months of kanamycin, isoniazid, prothionamide, gatifloxacin high-dose, clofazimine, ethambutol and pyrazinamide, followed by 5 months of gatifloxacin high-dose, clofazimine, ethambutol and pyrazinamide (MDR regimen, 9 months)

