#### Treatment:

*New cases:* Compared to standard regimen dosing of rifampicin is doubled, while standard dose isoniazid, pyrazinamide and ethambutol are maintained, i.e. 2 months of HRhZE followed by 4 months of HRh (6 months)

*Retreatment cases:* retreatment cases randomized to the intervention arm receive the same care as new cases in the same arm.

Any patients with *MDR TB detected* at any time will be switched to 4 months of KHPtoGCEZ followed by 5 months of GCEZ (MDR regimen)

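### End-of-treatment weight gain (SAP 7.6) is measured at month 6 in one arm and month 8 in the other for retreatment cases, and the change score is compared without adjustment

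*SAP*

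**What the plan says.** SAP 7.6 is the only specification of this comparison, because the objective was added in the SAP (section 2.2) and is not in the protocol. It reads: "Weight gain between enrollment and end of treatment will be compared between the two regimens using the t-test or Wilcoxon rank sum test". No covariate, stratification or fixed month is named.

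Treatment length comes from SAP 2.1, under Treatment:

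- New cases, control: "Cat. 1 regimen, 6 months".
- New cases, intervention: "2 months of HRhZE followed by 4 months of HRh (6 months".
- Retreatment cases, control: two months with streptomycin, "followed by 1 month of HRZE and 5 months HRE (Cat. 2 regimen, 8 months".
- Retreatment cases, intervention: "retreatment cases randomized to the intervention arm receive the same care as new cases in the same arm", hence 6 months.

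The last weight on treatment is taken at V8, which protocol 5.3 describes as "Visit after 6 months (or 8 months for Cat. 2) V8: intervention + control arm". The schedule in protocol 5.1 has no month-6 visit for patients on the 8-month regimen. Weight is scheduled in both arms at enrolment, weeks 2 and 4, and months 2, 3, 4 and 5.

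Elsewhere the SAP allows for the longer control regimen. Section 1 times the end-of-treatment data cut at 9 months after recruitment so as to cover all treatment data, "including 8 months of treatment for retreatment cases in the control arm". SAP 7.6 makes no such allowance.

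**The concern.** In the retreatment stratum, the arm decides not only what the patient receives but also when the patient is weighed. Randomisation cannot balance this, because the two-month gap follows from the assigned regimen. If weight is still rising late in treatment, control retreatment cases show more gain simply because they are weighed later, and part of any regimen difference is observation time. The Wilcoxon alternative has the same problem as the t-test.

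The test in 7.6 also uses less information than the SAP uses elsewhere. The primary model (SAP 6) and the tests for serious adverse events and liver toxicity (SAP 8.2) adjust for hospital and stratum, and the trial is randomised from separate lists for new and retreatment cases (protocol 4.4). The weight comparison uses neither factor, and it uses enrolment weight only by subtraction.

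At stake is the reading of one secondary comparison. A real difference could be blurred or a spurious one suggested, and some precision already paid for is lost.

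**Working it through.** The documents state no effect size, SD or power for weight gain, so there is no figure of the plan's own to reproduce.

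**Inputs from the documents**

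- Treatment length of retreatment cases: 8 months control, 6 months intervention (SAP 2.1).
- Treatment length of new cases: 6 months in both arms (SAP 2.1).
- Patients per arm: 500 (protocol 4.3).
- Retreatment share r: not given for the trial. The national figure is 7366 of about 100,000 smear-positive cases (protocol 1.1), so r = 7366/100,000 = 7.4%.

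**Assumptions, not in the documents**

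- Gain g over months 6 to 8: 0.1 to 0.5 kg per month.
- Range for r: 5% to 20%.
- SD of weight change: 3 to 5 kg.
- Baseline to follow-up correlation ρ: 0.7 to 0.9, with equal SDs at both times.

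**Step 1. Difference in measurement time.** Retreatment: 8 − 6 = 2 months. New: 6 − 6 = 0.

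**Step 2. Timing artefact within the retreatment stratum** = 2 × g.

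- g = 0.1: 0.2 kg
- g = 0.5: 1.0 kg

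**Step 3. Timing artefact in the pooled comparison** = 2 × g × r, since only the retreatment fraction of the control arm has the extra two months.

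| r | g = 0.1 | g = 0.5 |
|---|---|---|
| 5% | 0.010 kg | 0.050 kg |
| 7.4% | 0.015 kg | 0.074 kg |
| 20% | 0.040 kg | 0.200 kg |

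**Step 4. Size relative to the noise.** SE of the pooled difference = SD × √(2/500), which is 0.19 kg at SD 3 and 0.32 kg at SD 5.

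- At r = 7.4%, the artefact is at most 0.074/0.19 = 0.39 SE. With no true regimen effect, a two-sided 5% test would reject in 5.0% to 6.8% of trials.
- At r = 20%, g = 0.5 and SD 3, it is 0.20/0.19 = 1.05 SE, and the test would reject in about 18% of trials.

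**Step 5. Would adjusting for stratum alone remove it?** No. The extra time belongs to one arm within one stratum. A main effect for stratum does not separate that from the arm effect. Only a common measurement time sets 2 × g to 0.

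**Step 6. Value of baseline adjustment.** With equal SDs σ, the change score has variance 2σ²(1 − ρ) and ANCOVA has residual variance σ²(1 − ρ²). The ratio is (1 + ρ)/2.

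- ρ = 0.7: 0.85, a 15% reduction
- ρ = 0.8: 0.90, a 10% reduction
- ρ = 0.9: 0.95, a 5% reduction

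**The case against.** The strongest reply is that the objective compares two regimens, and for retreatment cases the regimens differ in length by design. Gain over each complete regimen is then a coherent contrast, and it is biased only if the target is weight at a fixed time, which neither document says. This stands in part. It is why the point is one of confounding between regimen and observation time in one stratum, and not of a proven bias. But SAP 7.6 does not say that a whole-regimen contrast is intended, and a reader of the pooled result could not tell the two apart.

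The direction is also conditional. The artefact runs against the intervention only if patients still gain weight in months 6 to 8, and the documents do not show that they do.

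A reader might infer that the test disregards enrolment weight. It does not: weight gain is a change score, so enrolment weight is subtracted. Leaving it out as a covariate, and leaving out stratum and hospital, costs precision under randomisation and does not bias the comparison.

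The plan has a partial safeguard. Protocol 8.3.5 promises a description of all data separately for new and retreatment cases, which would expose the affected stratum, and new cases are aligned at month 6. But that split is descriptive, SAP 6.1 limits subgroup analyses to the primary endpoint, and the pooled test in 7.6 is unchanged.

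Finally, the consequence is limited. Protocol 8.1 puts estimation ahead of formal testing, and the go/no-go criteria (protocol 2.1 and 8, SAP 1) use neither weight nor fever. That is fair, and it sets the severity.

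**Conclusion.** The point holds as a minor one. The two-month difference in measurement time for retreatment cases follows directly from the SAP's own regimens and the visit schedule, and nothing in the plan removes it from the comparison in 7.6. Under the assumed gain of 0.1 to 0.5 kg per month, it is worth 0.2 to 1.0 kg within the retreatment stratum.

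A reader might infer that the overall weight comparison is seriously distorted. The documents do not support that. At the only documented share, 7.4% nationally, the pooled artefact is about 0.015 to 0.074 kg and the error rate stays near its nominal level. A figure such as 0.20 kg needs an assumed share of 20% together with the top of the assumed gain. Screening out rifampicin-resistant retreatment cases before enrolment (protocol 4.2 and 5.3) would, other things equal, lower the trial's share. Since the trial's own share is not stated, a small pooled effect is likely but not assured.

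The missing adjustment is a loss of precision of about 5% to 15% in variance at ρ = 0.9 to 0.7, and less at higher correlations (2.5% at ρ = 0.95).

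A reader might also infer that the fever comparison is invalid, because SAP 7.6 says only "Fever resolution after two weeks of treatment will be compared between the two regimens" by a chi-squared or Fisher's exact test and names no denominator. That is missing detail and no more. Resolution implies fever at the start, and the SAP does not say that patients without fever at enrolment will be counted.

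**What to change.** In SAP 7.6, make the main comparison weight at month 5 (V7) by ANCOVA with enrolment weight, randomisation stratum and hospital as covariates. V7 is the last scheduled weight taken at the same time in both arms and both strata, so the timing artefact becomes 0. Report gain from enrolment to end of treatment descriptively by arm and stratum, with the month of measurement shown. State how patients without a month-5 weight, and those switched to the 9-month MDR regimen, are handled.

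The same edit can name the fever threshold at enrolment that defines who can resolve fever. This is a clarification only.

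The cost is SAP wording, as all the weights are already scheduled. The one real downside is that the main comparison omits the last month of the 6-month regimens, for new cases as well, although they have no timing problem. The descriptive end-of-treatment report keeps that information.
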